5.1 Informed consent and consent to the processing of personal data

The study protocol, any protocol amendment, informed consent, consent to the processing of personal data and any other information for patients must be approved by the Ethics Committee.

To participate in the study, each patient must provide written informed consent as well as consent to the processing of their personal data. In case it will be not possible to acquire informed consent (e.g. deceased or untraceable patients), data will be collected anonymously, meaning that possible patient identifiers will be removed.

5.1.1 Methods of acquiring informed consent and consent to the processing of personal data

Informed consent will be obtained by local investigators in collaboration with the attending physicians. For the retrospective cohort, it will be obtained during the standard scheduled follow-up visits. However, for those cases where it will not be possible to acquire consent, anonymized data (thus lacking a key that indirectly identifies the patient) may be recorded in the CRF. For the prospective cohort, informed consent will be administered to the patients at the enrolment. Only patients who will provide informed consent will be enrolled.

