4.4.1 Inclusion Criteria

- Diagnosis of B cell malignancies or previous treatment with B cell targeting therapies.
- Diagnosis of proven SARS-CoV-2 infection confirmed by a PCR test (only the first infection during the study period will be considered, re-infection will be counted as a secondary endpoint).
- Provision of signed and dated informed consent.

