4.5 Study duration

The study will be composed by:

- a prospective recruitment period of 1 year after Ethics Committees' approvals and directorates' permissions to conduct the study (during which retrospective data will also be collected);
- Follow-up period of 120-days from the diagnosis of SARS-CoV-2 infection;
- Data collection and analysis, that will last 6 months

For an overall duration of approximately 22 months

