4.8 Statistical Analysis Plan

Patients' characteristics will be summarized using absolute frequencies and percentages (categorical variables) and mean±standard deviation or median and interquartile range (scale variables, according to their distribution).

The prevalence of persisting SARS-CoV-2 infection among the immunocompromised patients will be obtained as the ratio of the number of patients with evidence of persisting SARS-CoV-2 infection on the total number of enrolled patients.

As for the analysis of risk factors for persisting COVID, comparisons between COVID-persistent and non-persistent patients will be carried out by means of survival analyses for all outcomes expressed as durations (time-to-event analyses). These outcomes will be compared by estimating Kaplan-Meier curves, calculating log-rank tests and multiple Cox regressions in which COVID persistence will be the main risk factor and including the confounders and effect modifiers listed below.

- Age
- Sex
- Comorbidities (Charlson Comorbidity Index)
- Underlying hematologic disease state
- Chemotherapy treatments performed
- Duration of Hospital stay
- Admissions to intensive care
- Days with central venous catheter
- Bacterial and fungal superinfections
- Vaccination status
- Previous SARS-CoV-2 infections
- Serological status (anti-SARS-CoV-2 antibodies)

Re-infection and imaging alterations rates will be calculated as the ratio of the number of events to the overall number of patients, and the comparison between persisters and non-persisters will be carried out by calculating the corresponding risk ratios. A multiple logistic regression model will assess the relationship between exposure and re-infection (image alteration) net of the potential confounders.

For secondary aims, the secondary endpoints will be described just for the patients with persisting COVID, categorical variables will be reported as number and relative

frequencies, continuous variables will be reported as mean±SD or median and IQR according with their distribution.

5. Administrative procedures and declarations

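### Prospective patients enter at consent but survival is counted from diagnosis, with no delayed entry: prospective 120-day mortality is biased downward and the persister hazard ratio probably upward

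*Combined protocol and SAP*

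**What the plan says.** Prospective entry is set in section 5.1.1: "For the prospective cohort, informed consent will be administered to the patients at the enrolment", and then "Only patients who will provide informed consent will be enrolled". No maximum interval from test to consent is given.

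For the retrospective cohort the same section says "For the retrospective cohort, it will be obtained during the standard scheduled follow-up visits". Where that fails, "anonymized data (thus lacking a key that indirectly identifies the patient) may be recorded in the CRF".

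Two other places bear on who gets in. The general text of section 5.1 says "In case it will be not possible to acquire informed consent (e.g. deceased or untraceable patients), data will be collected anonymously", without limiting this to either cohort. Section 4.4.1 lists "Provision of signed and dated informed consent" as an inclusion criterion, with no exception.

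The clock is set in section 4.5: "Follow-up period of 120-days from the diagnosis of SARS-CoV-2 infection". Section 3.3 defines time 0 as the day of the first positive test and requires PCR positivity at day 21 or later for persistence. All-cause 120-day mortality is a secondary endpoint.

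Section 4.8 compares persisters and non-persisters by "estimating Kaplan-Meier curves", log-rank tests and Cox regression. It states no delayed entry, and recruitment mode is not among its 12 listed covariates.

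**The concern.** A patient who is enrolled only on consenting cannot, in the data, die before consenting. If risk time nevertheless starts at the positive test, the days in between are counted as at risk although no death could be observed in them. This is left truncation, and ignoring it biases mortality downward.

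Under section 5.1.1 the two cohorts differ in this respect. A death between test and consent removes a prospective patient from the study, while the same death in a retrospective patient may be recorded. Pooling them mixes two selection rules.

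The persister comparison is affected as well, because the losses need not be even. A patient who dies before day 21 cannot meet the persistence definition, so early losses come out of the non-persister group. Its apparent mortality falls and the hazard ratio for persistence rises.

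**Working it through.** **1. The plan's own figure.** Section 4.4.3 gives N = 933 and 40 events for 97% v 93% survival, two-sided alpha 0.05, 80% power, allocation ratio k = 0.43, Freedman method.

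- HR = ln(0.93)/ln(0.97) = 2.383
- E = (1.960 + 0.842)² × (1 + k·HR)² / [k·(HR − 1)²] = 39.1
- Event probability = (0.03 + 0.43 × 0.07)/1.43 = 0.0420, so N = 39.1/0.0420 ≈ 931

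This agrees with 933. Power at N = 1,000 is 82.7%. The sample-size table is not in dispute.

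**2. Deaths lost before consent.** The documents give neither the test-to-consent gap nor the timing of deaths, so both are assumed. Let m be 120-day mortality, H = −ln(1 − m) and d the consent day. Cumulative hazard to day d is H_d = H·(d/120)^s, with s = 1 for a constant hazard and s = 0.5 for a front-loaded one. The share of deaths lost is (1 − exp(−H_d))/m. For m = 3%:

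| Consent day | Lost, constant hazard | Lost, front-loaded |
|---|---|---|
| 0 | 0% | 0% |
| 3 | 2.5% | 16% |
| 7 | 6% | 24% |
| 14 | 12% | 35% |
| 21 | 18% | 42% |

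**3. Apparent non-persister mortality in the prospective part.** This is 1 − exp(−(H − H_d)). With d = 7 and H = 0.03046:

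- Constant: H_d = 0.00178, giving 2.83% instead of 3%.
- Front-loaded: H_d = 0.00736, giving 2.28% instead of 3%.

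**4. Hazard ratio.** Assume half of each group is prospective, consent is at day 7, and all lost deaths are non-persister deaths (since d < 21). Persister mortality stays at 7%.

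- Constant: non-persister mortality = 0.5 × 3% + 0.5 × 2.83% = 2.91%; HR = ln(0.93)/ln(1 − 0.0291) ≈ 2.45.
- Front-loaded: 0.5 × 3% + 0.5 × 2.28% = 2.64%; HR = ln(0.93)/ln(1 − 0.0264) ≈ 2.71.

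Both compare with 2.38 under full capture. Nominal Freedman power at N = 1,000 rises to about 85% and 90%, because the apparent effect is larger.

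**5. Prevalence.** With 350 prospective non-persisters, patients lost = 350 × (1 − exp(−H_d)) = 0.6 to 2.6. Prevalence moves from 30.0% to 300/999.4 = 30.02%, or to 300/997.4 = 30.08%. The 95% half-width is 1.96 × √(0.3 × 0.7/1000) = 2.8 points.

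**6. Who is captured: three texts, three results.**

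- Section 5.1, general sentence: patients who die before consent can be kept in both cohorts.
- Section 4.4.1, read literally: they are lost from both.
- Section 5.1.1: they may be kept retrospectively and are lost prospectively.

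**The case against.** The strongest objection is that the gap is unknown. The protocol says only that consent is taken at enrolment, and if that is always the day of the positive test the effect is zero. This stands as a limit on size. It does not remove the point: nothing requires same-day consent, section 4.4 includes outpatients, and without a recorded consent date nobody could show that the gap was short.

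It can also be said that the general sentence in section 5.1 already covers prospective patients who die. That sentence is unrestricted, but section 5.1.1 gives the cohort-specific rule and closes the prospective route. A reader might go further and take it as settled that early deaths are lost in one cohort only. The documents do not support that certainty: the retrospective exception is permissive, and section 4.4.1 allows no exception at all.

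A reader might also infer a loss of power from the missing deaths. If both groups lost deaths alike, power in the half-prospective, 7-day illustration would fall from 82.7% to between 81.6% and 77.8%. But deaths before day 21 cannot be persister deaths, so even losses would need many consents after day 21, which nothing in the documents suggests. The expected harm is a biased hazard ratio.

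Finally, the prevalence denominator is selected in the same way, which might suggest harm to the primary endpoint. The shift is under 0.1 point in the illustration, far inside the sampling error.

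**Conclusion.** The point holds. On the most specific reading of the consent text, prospective time from test to consent is event-free by design but is analysed as time at risk, so prospective 120-day mortality is biased downward. The size cannot be derived from the documents.

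The likely effect on the persister comparison is an inflated hazard ratio, from 2.38 to about 2.45 to 2.71. This rests on assumptions: half the cohort prospective, consent at day 7, a constant to front-loaded hazard, and all losses among non-persisters. If many patients consent after day 21, persister deaths are lost too and the direction is less certain. The guaranteed survival of persisters to day 21 under their own definition is a separate matter that pulls the hazard ratio the other way, so the net bias may be smaller or reversed.

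The effect on prevalence is negligible, and no power loss should be claimed. Mortality is a secondary endpoint, but it is the one on which section 4.4.3 bases its power calculation, so the analysis should be corrected.

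**What to change.** 1. Reconcile sections 4.4.1, 5.1 and 5.1.1, stating for each cohort whether patients who die before consent are included.
2. Record the consent date, and flag records entered by the anonymised route.
3. In section 4.8, state diagnosis as the time origin and use delayed entry at the consent date for every patient whose inclusion depended on surviving to consent. That means prospective patients, and retrospective patients too if deceased non-consenters are not captured.
4. Stratify the survival models by recruitment mode, and report mortality and prevalence by mode.

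Step 1 has to come first. If signed consent is required of retrospective patients without exception, anyone consenting after day 120 contributes no risk time to 120-day mortality under delayed entry.

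The cost is one date field, an entry option in the survival set-up, and fewer patients at risk in the first days, hence wider early confidence bands. Delayed entry removes the guaranteed survival time only. It does not correct for patients too ill to consent, and it does not restore lost patients to the prevalence denominator, which is why results by mode are needed as well.

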5.2 Study – specific insurance

Considering the nature of the study, a specific insurance is considered unnecessary.

5.3 Amendments to the protocol and changes to the conduct of the study

If during the enrolment period, the principal and local investigators will agree that any deviation from the original protocol is needed to reach the predefined sample size and/or to avoid bias in the assessment of outcomes, the protocol will be revised and an amendment will be submitted to Ethic Committees.

5.4 Conclusion of the study

After the lock of database, preliminary results will be shared with all the investigators in order to plan publication and other dissemination activities. These results will be used to communicate to local Ethic Committees the conclusion of the study.

5.5 Publication policy

Preliminary results will be revised by all the investigators in order to refine statical analysis, and to plan publication and other dissemination activities (presentation of results at International Congresses of Infectious Diseases and Transplant Societies).

For authorship, Recommendations for the Conduct, Reporting, Editing and Publication of Scholarly Work in Medical Journals (ICMJE Recommendations) will be followed. The ICMJE recommends that authorship be based on the following criteria:

- Substantial contributions to the conception or design of the work; or the acquisition, analysis, or interpretation of data for the work; AND
- Drafting the work or revising it critically for important intellectual content; AND
- Final approval of the version to be published; AND
- Agreement to be accountable for all aspects of the work in ensuring that questions related to the accuracy or integrity of any part of the work are appropriately investigated and resolved.

According to the rules of good scientific practice, the principal investigator can claim the position of last author if he/she is not already first author. In the case of several research project leaders, they should agree on the last authorship among themselves at an early stage; in this context, shared first and last authorships should also be considered. As a rule, the "corresponding author" should be the research project leader with primary responsibility. The middle group of co-authors will be included according to contribution to the manuscript as the ICMJE recommendations.

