4.4.3 Population size of the study and statistical power

According to the records of the Haematology Unit of IRCCS AOU of Bologna, from January 2022 to December 2022, 250 patients with underlying B cell malignancies have been diagnosed with SARS-CoV2 infection and we estimate that approximately 30% had viral shedding longer than 21 days. Thus, we deem that at the end of the study period, approximately 500 patients will be enrolled from IRCCS AOU of Bologna of which about 150 with prolonged infection. Considering the epidemiology of the other participating centers, we expect to reach an overall cohort of about 1000 immunocompromised patients with SARS-CoV-2 infection, with approximately 300 prolonged infections.

Power analysis carried out using Stata v.17.0 showed that a sample size of 1,000 allows to obtain power=80% and alpha=0.05 for a log-rank test comparing 120-days mortality, with a 300/700 allocation ratio, when the difference in mortality rates is at least 4% and mortality rate in the non-persistent COVID is as low as 3%, or when the difference in mortality rates is at least 5% and mortality rate in the non-persistent COVID is at least 4%.

Estimated sample sizes for two-sample comparison of survivor functions
 Log-rank test, Freedman method
 H0: HR = 1 versus Ha: HR != 1

alpha	power	N	N1	N2	nratio	E	delta	hratio	s1	s2	Pr_E
.05	.8	897	627	270	.43	59	2.054	2.054	.95	.9	.06503
.05	.8	1,343	939	404	.43	84	1.839	1.839	.95	.91	.06203
.05	.8	2,282	1,596	686	.43	135	1.626	1.626	.95	.92	.05902
.05	.8	4,900	3,426	1,474	.43	275	1.415	1.415	.95	.93	.05601
.05	.8	18662	13050	5,612	.43	990	1.206	1.206	.95	.94	.05301
.05	.843	.	1	1	.95	.95	.
.05	.8	561	392	169	.43	33	2.581	2.581	.96	.9	.05804
.05	.8	768	537	231	.43	43	2.31	2.31	.96	.91	.05503
.05	.8	1,140	797	343	.43	60	2.043	2.043	.96	.92	.05203

	.05	.8	1,918	1,341	577	.43	94	1.778	1.778	.96	.93	.04902	
	.05	.8	4,070	2,846	1,224	.43	188	1.516	1.516	.96	.94	.04601	
	.05	.8	15304	10702	4,602	.43	659	1.257	1.257	.96	.95	.04301	
	.05	.8	367	256	111	.43	19	3.459	3.459	.97	.9	.05105	
	.05	.8	471	329	142	.43	23	3.096	3.096	.97	.91	.04804	
	.05	.8	638	446	192	.43	29	2.737	2.737	.97	.92	.04503	
	.05	.8	933	652	281	.43	40	2.383	2.383	.97	.93	.04203	
	.05	.8	1,545	1,080	465	.43	61	2.031	2.031	.97	.94	.03902	
	.05	.8	3,221	2,252	969	.43	116	1.684	1.684	.97	.95	.03601	

s1, s2 = survival rates in groups 1 and 2
 N1, N2 = sample size required in groups 1 and 2.

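### Sections 5.4 and 5.5 let investigators refine the analysis after seeing post-lock results, and nothing requires such changes to be marked as post hoc

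*Combined protocol and SAP*

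**What the plan says.** All references are to the combined protocol and SAP.

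- **5.4 Conclusion of the study**, on timing: "After the lock of database, preliminary results will be shared with all the investigators in order to plan publication and other dissemination activities".
- **5.5 Publication policy:** "Preliminary results will be revised by all the investigators in order to refine statical analysis". The same sentence goes on to planning publication.
- **5.3 Amendments:** the only change-control clause opens "If during the enrolment period, the principal and local investigators will agree that any deviation from the original protocol is needed". Its reasons are reaching the sample size and avoiding biased outcome assessment.
- **4.8 Statistical Analysis Plan, duration outcomes:** log-rank tests, Kaplan-Meier curves and "multiple Cox regressions in which COVID persistence will be the main risk factor and including the confounders and effect modifiers listed below". Twelve items follow, from age to serological status.
- **4.8, re-infection and imaging:** crude risk ratios, then "A multiple logistic regression model will assess the relationship between exposure and re-infection (image alteration) net of the potential confounders".
- **4.8, prevalence:** "the ratio of the number of patients with evidence of persisting SARS-CoV-2 infection on the total number of enrolled patients", with no test or interval.
- **4.4.3 Population size and power:** "a sample size of 1,000 allows to obtain power=80% and alpha=0.05 for a log-rank test comparing 120-days mortality". This is the only place where an alpha is fixed.

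**The concern.** Taken together, 5.4 and 5.5 set an order: the database is locked, results are produced and circulated to every investigator, and the analysis is then refined. A nominal 5% test or 95% interval keeps its stated property only if the model was not picked in the light of its own result. If the covariate set, an interaction or the compared outcomes change after the results are known, the reported p-value no longer describes the procedure that produced it. A reader of the paper could not tell which associations were planned. Section 2.2 hopes that the results will inform clinical practice and future interventional studies, so the distinction matters to those who will use them.

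**Working it through.** **1. Is the refinement limited anywhere?**

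- Data cleaning does not explain it. Under 4.7, queries are resolved before lock, and 5.4 places the results after lock.
- The amendment route in 5.3 covers needs agreed during enrolment and does not reach analysis changes after lock.
- No section freezes the SAP before results are seen, or asks for later changes to be documented or labelled.

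**2. What the stated alpha assumes.** The power table in 4.4.3 uses the Freedman log-rank method, two-sided alpha 0.05, power 80% and allocation ratio k = 0.43:

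HR = ln(s2)/ln(s1)

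E = (1.960 + 0.842)² × (1 + k·HR)² / [k(1 − HR)²]

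Pr_E = [(1 − s1) + k(1 − s2)]/(1 + k), and N = E/Pr_E

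| s1 / s2 | HR | E | Pr_E | N computed | N stated |
|---|---|---|---|---|---|
| 0.97 / 0.93 | 2.383 | 39.14 | 0.04203 | 931 | 933 |
| 0.96 / 0.91 | 2.310 | 42.25 | 0.05503 | 768 | 768 |
| 0.95 / 0.90 | 2.054 | 58.27 | 0.06503 | 896 | 897 |

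The plan's figures reproduce. With N = 1,000 split 300/700, power is Φ(√(E·k)·(HR − 1)/(1 + k·HR) − 1.96), with k = 300/700 and E = 1,000 × Pr_E. This gives 0.83 for mortality of 3% against 7%, and 0.89 for 4% against 9%. These figures describe one fixed, unadjusted test. They say nothing about a model chosen afterwards.

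**3. What is left to choose.**

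| Item | Fixed | Open |
|---|---|---|
| Cox covariates | 12 items named (4.8) | which are confounders and which effect modifiers; coding; interactions |
| Logistic covariates | none named for this model | the whole set |
| Secondary endpoints | listed in 3.3 | compared between groups (3.2), or described in persisters only (end of 4.8) |
| Exposure | defined in 3.3 | – |
| Crude prevalence, log-rank, crude risk ratios | as written in 4.8 | – |

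Several listed covariates (length of stay, intensive care admission, superinfection) can arise after infection, so keeping or dropping them can move the estimate.

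**4. How much could selection matter?** The documents give neither the number of models that might be tried nor the covariate imbalance between groups, so any figure is an illustration under assumptions. A null simulation used:

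- N = 1,000, split 300/700, with 4.2% events (Pr_E from the 0.97/0.93 row);
- 12 normal covariates, unrelated to outcome, each shifted between groups by 0, 0.3 or 0.5 SD (assumed);
- a linear-model t-test, |t| > 1.96, standing in for Cox or logistic regression;
- 26 adjustment sets: unadjusted, all 12, each alone, each left out in turn (1 + 1 + 12 + 12); and 126 sets when 100 random subsets are added;
- 1,000 replicates.

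| Shift (SD) | Unadjusted | All 12 | Best of 26 | Best of 126 |
|---|---|---|---|---|
| 0 | 0.038 | 0.035 | 0.046 | 0.048 |
| 0.3 | 0.056 | 0.051 | 0.116 | 0.147 |
| 0.5 | 0.049 | 0.056 | 0.153 | 0.244 |

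The Monte Carlo standard error is about √(0.05 × 0.95/1,000) = 0.007 near 5%, and √(0.244 × 0.756/1,000) = 0.014 at the top of the table. Either fixed model stays near 5%. With balanced covariates, choosing the best set adds about one percentage point and the rate stays below 5%. With imbalance it rises to about 12–24%.

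**The case against.** The sentence sits in a publication policy and its English is loose. Refinement may mean no more than model checks, clarifications or corrections, and no section says that a preferred model will be picked on its result. Section 5.4 gives the purpose of sharing as planning publication, so it supports the timing only. The study is observational, its primary objective is descriptive, and investigators in such studies routinely look at results and explore further.

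Much of this stands. It lowers the weight of the point and rules out any suggestion of intent. It does not remove the point: 5.5 makes refinement of the analysis a stated purpose of reviewing the results, comparative tests and a power calculation at alpha 0.05 are planned, and no section asks for changes to be labelled.

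Three stronger readings are tempting, and the documents do not support them.

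- *All p-values and intervals become meaningless.* The crude analyses keep their properties on this point if run as written. Section 4.8 plans no confidence intervals, so loss of coverage concerns only intervals reported later from changed models.
- *The exposure definition is also open.* Section 3.3 defines it: symptoms or signs together with a positive PCR at 21 days or more. The 30% in 4.4.3 counts viral shedding alone, but it is a planning estimate and not a rival definition.
- *The false-positive rate follows from 1 − 0.95^k for k models tried.* That formula needs independent specifications. Adjusted models fitted to the same patients and outcome are correlated, and the simulation shows the result can be close to no inflation.

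**Conclusion.** The concern holds in a limited form. The plan provides for changing the analysis after post-lock results are seen and does not require planned and results-driven analyses to be kept apart. The analyses exposed are the adjusted Cox and logistic models, and the choice of which secondary endpoints are compared. Any of these changed after its results are known loses its nominal error rate and coverage.

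The size cannot be derived from the documents. The range from essentially no inflation to about 12–24% rests on an assumed imbalance of 0 to 0.5 SD in every covariate, deliberate reporting of the most favourable of 26 or 126 sets, and a linear stand-in for the planned models. Imbalance is plausible because the groups are observed and not randomised, but the plan gives no figure for it. The matter should be corrected before analysis; it does not put the primary prevalence estimate in doubt.

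**What to change.** 1. In 5.5, delete the words that make refinement of the statistical analysis a purpose of reviewing preliminary results. Planning of publication can stay.
2. In 4.8, settle the open choices: the role of each of the 12 covariates, their coding, any interactions, the covariates of the logistic model, and whether each secondary endpoint is compared between groups or described in persisters only, so that 3.2 and the end of 4.8 agree.
3. Date that SAP before any comparison of persisters with non-persisters is run, and no later than database lock. Lock alone is a weak safeguard: recruitment reaches back to January 2022 (4.3), and under 4.7 the principal investigator has access to all data during collection.
4. State that any analysis added or changed afterwards is reported as post hoc, beside the prespecified result.

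The text is short and no new data are needed. The real cost is that the modelling decisions left open in 4.8 must be made earlier, which takes some statistical work. Exploration remains allowed if it is labelled.
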